7.5 Dealing with Multiple Values on the Same Day

If multiple measurements are made on the same day for a laboratory parameter or a vital signs parameter, the average of the values will be used in analyses. For summaries of shifts from Baseline and potentially significant values, multiple values on the same day will not be averaged; all values will be considered for these analyses.

If multiple measurements for a particular parameter other than a laboratory parameter and a vital signs parameter are made on the same day for the same subject, the most conservative (worst) measurement will be used in analyses.

7.6 Definitions and Conventions of MBL Volume and Bleeding Days

7.6.1 MBL Volume

The MBL volume is based on validated and non-validated sanitary products unless otherwise specified (for some sensitivity analysis, the MBL volume will be based on validated sanitary products only).

Baseline MBL volume is based on observed AH data only. No imputation will be made for Baseline MBL volume.

7.6.1.1 Observed MBL Volume Over a Window

If there were observed AH data between two study visits (Product Collection Visit or site visit with UBY completed), then the MBL volume on the days with observed AH data will be the observed AH data and the MBL volume for the rest of days between the two study visits will be imputed as 0 by AH data.

UBQ responses indicate if a subject has any bleeding or spotting since the last study visit (Product Collection Visit or site visit with UBQ completed). If observed evaluable AH data is available over a window, then the UBQ will not be used.

If the AH data is reported as "NVB" (no visible blood, discarded without assay), "NO BLEED" (no collection due to no bleeding as indicated by subject or clinical site on assay requisition form), or "TL BQL" (total below low limit of quantitation), the numeric value for the AH data will be imputed as 0. If the AH data is reported as other character value ("NULL," "IN ERROR," "NO DATA," and etc.), the corresponding numeric value for the AH data will be set as missing.

The observed MBL volume over a window (such as the Final Month, Month 1 [Study Days 2 – 28], Month 2 [Day 29 – Day 56], Month 3 [Day 57 – Day 84], Month 4 [Day 85 – Day 112], Month 5 [Day 113 – Day 140], and Month 6 [Study Days 141 – 168]) is defined as follows:

- If a subject has any evaluable AH data reported in the window, then the subject's MBL volume in this window will be the total combined observed AH data of validated and non-validated sanitary products over this window.
- If a subject is missing AH data or all AH data are unevaluable in the window and the UBQ is completed and indicates no bleeding or spotting, "Subject only had spotting that did not require the use of sanitary products" or "There was no visible blood on the sanitary products" and covers this window, then:

A value of 0 will be assigned to the MBL volume over this window.
- If a subject is missing AH data or all AH data are unevaluable in the window and the UBQ is completed with no bleeding or spotting or "Subject only had spotting that did not require the use of sanitary products" or "There was no visible blood on the sanitary products" indicated but UBQ does not cover the full window, then:

A value of 0 will be assigned to the MBL volume over this window if the days not covered by UBQ response as described above have AH imputed MBL volume (see first paragraph in Section 7.6.1.1) being 0 for those days.

If there is still no value assigned after the imputation procedure described above, the observed MBL volume over the window is considered missing.

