* Study site must consult AbbVie for approval to collect sanitary products for additional menstrual cycles in screening.

There may be instances when a 4th cycle needs to be collected due to certain circumstances. Study Site must also consult AbbVie for approval in the event a 4th cycle is needed to determine eligibility based on MBL.

Sites will contact the Interactive Response Technology (IRT) at the Screening Cycle 2 Product Collection Visit to register the date of the visit for the first subject who completes the Screening Cycle 2 Product Collection Visit. The registration of this visit will trigger the initial shipment of study drug to the study site.

Sanitary Product Collection During the Treatment Period

During the Treatment Period, Subjects will continue to collect sanitary products on all days with menstrual bleeding or spotting.

As in Screening, sanitary products collected during the Treatment Period will be returned by the Subject within approximately 5 days after cessation of menstrual bleeding or spotting and a venous sample will be obtained at either a scheduled monthly visit or at a Product Collection Visit, as appropriate.

Treatment Period Product Collection Visits

Product Collection Visits are only necessary if a monthly visit is not scheduled to occur within approximately 5 days after cessation of menstrual bleeding or spotting. During the Product Collection Visits, subjects will have a venous blood sample, urine pregnancy test, vital signs, contraception counseling, as well as adverse event and concomitant medication assessment. Product Collection Visits during the Treatment Period should be

numbered in sequential order (e.g., Product Collection Visit 1, Product Collection Visit 2, etc.) and entered into the eCRF.

Subjects who do not return a sanitary product collection keg at a site visit (scheduled monthly visit, PCV or Unscheduled Visit) will be administered the UBQ by the Site Staff. The Site Staff will ask the subject if she had any bleeding or spotting since the previous visit. If the subject did have bleeding or spotting since the previous visit, the site staff will ask why the subject did not return sanitary products. Responses to these questions will be documented on the UBQ by the Site Staff.

Sanitary Product Collection During the Post-Treatment Follow-Up Period

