8.1.7.1.2 Derivation of Primary Efficacy Endpoint

The Final Month MBL volume will be derived as follows:

- If a subject has any AH data reported during the Final Month (i.e., she has at least 1 day of AH data during the last 28 days of treatment), then her primary endpoint will be based on AH data during the Final Month. The subject's Final Month MBL volume will be the total MBL volume which is the sum of the observed MBL volume over the last 28 days of treatment.
- If a subject is missing the Final Month AH data and the Uterine Bleeding Questionnaire is completed, then:
- A value of 0 will be assigned to the Final Month MBL volume if no bleeding or spotting, "Subject only had spotting that did not require the use of sanitary products" or "There was no visible blood on the sanitary products" is indicated on the Uterine Bleeding Questionnaire (Appendix G).
- Otherwise, the primary endpoint will be imputed using multiple imputation as described in Section 8.1.7.1.3.

A flow-chart showing how the primary endpoint will be derived is presented in Figure 7.

Figure 7. Flow-Chart for Deriving Primary Endpoint

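### An unusable blood-loss assay record counts as 0 mL in the primary endpoint whenever any other record in the window is evaluable

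*SAP*

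**What the plan says.** SAP 7.6.1.1 separates two kinds of non-numeric AH result. For NVB, NO BLEED and TL BQL, which indicate no visible, no reported or no quantifiable blood, "the numeric value for the AH data will be imputed as 0". For any other character value, with NULL, IN ERROR and NO DATA as examples, "the corresponding numeric value for the AH data will be set as missing". The codes in this second group are not defined.

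The same section then builds the window volume. The condition is "If a subject has any evaluable AH data reported in the window"; when it is met, the volume is the total of the observed AH data. The opening paragraph adds that, where AH data exist between two visits, "the MBL volume for the rest of days between the two study visits will be imputed as 0 by AH data". On the Uterine Bleeding Questionnaire (UBQ) it says: "If observed evaluable AH data is available over a window, then the UBQ will not be used".

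Protocol 8.1.7.1.2 has the same threshold: the Final Month volume comes from AH data if "she has at least 1 day of AH data during the last 28 days of treatment". Protocol 5.3.1.1 gives the UBQ to "Subjects who do not return a sanitary product collection keg at a site visit", so a returned but unusable collection normally has no UBQ. SAP 11.2.2 starts multiple imputation only when the observed Final Month volume is missing, and step 3 of 11.2.2.1 uses a non-missing volume as it stands.

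**The concern.** The SAP recognises that an unusable record is not a zero, then lets the summation rule make it one. A record of unknown volume, possibly from a bleeding day, ends up with the same value as NO BLEED. The sponsor expects such records: SAP Section 13, item 4, says that handling of character values was added in this version.

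The Final Month volume decides both parts of the primary endpoint and feeds the first ranked secondary endpoint. The monthly volumes feed the ranked changes to Months 6, 3 and 1. An understated total can make a non-responder a responder, and nothing in the planned output would show that it had happened.

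**Working it through.** **1. Tracing the rule.** Take a window with some evaluable AH values and one coded IN ERROR.
- Its numeric value is missing, so it drops out of the sum. If it is instead read as one of the remaining days between visits, it is set to 0. Either way it adds 0 mL.
- The window total is non-missing, so the UBQ is not consulted and 11.2.2.1 is not triggered.
- In SAP 11.2.3, LOCF, non-responder imputation and observed cases act only on a missing Final Month volume. Analysis 1 changes only the discontinuation rule, and analysis 5 only the product type. None deals with a partly unevaluable window.

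This creates a discontinuity. If all five days of a menses are unusable and no qualifying UBQ answer exists, the window is imputed. If four are unusable and the fifth reads 3 mL, the volume is 3 mL and she is a responder, unless the discontinuation rule applies.

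**2. One subject (illustrative values, Baseline 200 mL).** Daily volumes are 8, 55, 45, 18 and 6 mL, with the 55 mL day coded IN ERROR.
- True total: 8 + 55 + 45 + 18 + 6 = 132 mL; reduction 1 − 132/200 = 34%. Non-responder on both criteria.
- Total under the SAP: 132 − 55 = 77 mL; reduction 1 − 77/200 = 61.5%. Responder.

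**3. The plan's own power.** Inputs from SAP 4.3 and 3.0: 100 placebo and 200 E2/NETA subjects, 30% against 60%, two-sided 0.05. Power = Φ[(d − 1.96·se₀)/se₁].
- Pooled rate (30 + 120)/300 = 0.50; se₀ = √(0.25 × 0.015) = 0.0612.
- se₁ = √(0.21/100 + 0.24/200) = 0.0574.
- (0.30 − 0.120)/0.0574 = 3.13, so power is 99.9%. The stated minimum of 90% is met.

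**4. Trial level.** No failure rate is given, so let *f* be the assumed share of true non-responders who flip. Each rate becomes p + (1 − p)f. With the same *f* in both arms, the difference becomes 30(1 − f).

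| f | Placebo | E2/NETA | Difference (points) | Power |
|---|---|---|---|---|
| 0 | 30.0% | 60.0% | 30.0 | 99.9% |
| 1% | 30.7% | 60.4% | 29.7 | 99.9% |
| 2% | 31.4% | 60.8% | 29.4 | 99.9% |
| 5% | 33.5% | 62.0% | 28.5 | 99.8% |
| 10% | 37.0% | 64.0% | 27.0 | 99.5% |

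If flips occur in one arm only, for f = 1%, 2%, 5% and 10%:
- E2/NETA only: difference 30.4, 30.8, 32.0 and 34.0 points. With no true effect (30% in both arms), the two-sided rejection rate is 5.1%, 5.6%, 9.1% and 22.0%.
- Placebo only: difference 29.3, 28.6, 26.5 and 23.0 points.

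At the planned rates the difference widens only if 0.40 × f on E2/NETA exceeds 0.70 × f on placebo, a ratio above 0.70/0.40 = 1.75.

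**The case against.** The strongest reply is that the codes are undefined. They may mark empty or mis-entered records rather than failed assays. Subjects must also return worn products with no visible blood (Protocol 5.3.1.1), so a returned product does not prove bleeding. This stands. A reader might infer that known bleeding days are being zeroed; the documents support only records of unknown volume, some possibly from bleeding days.

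Nor does the SAP say whether a code applies to a day or to a whole collection. If a whole collection fails and is the only one in the window, the window goes to imputation as intended, absent a qualifying UBQ answer. The defect then needs a second, evaluable collection in the same 28 days. That narrows how often it bites but does not remove it.

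Baseline MBL also uses observed AH data without imputation (SAP 7.6.1), so an unusable screening record lowers Baseline and makes the 50% criterion harder. This is a partial offset for some women, not a correction.

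A reader might also infer that most women who bleed in the Final Month are on placebo. The planned figures do not show that: expected non-responders are 0.40 × 200 = 80 on E2/NETA and 0.70 × 100 = 70 on placebo, and responders may bleed too. Only the non-responder proportion is higher on placebo.

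**Conclusion.** The point holds as a defect in the derivation rule that should be corrected; it does not threaten the trial's conclusion. As written, an unusable record adds 0 mL to any window with another evaluable value. The effect on a woman's post-baseline volume is always downward, so it can create responders and understate volume in the ranked MBL endpoints.

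The trial-level size cannot be computed without a failure rate. Under equal flipping, both responder rates are inflated and the difference shrinks: by 1.5 points at f = 5%, and by 3 points at 10% with power still 99.5%. Equal *f* is a simplification, since it also depends on how far above the thresholds non-responders lie in each arm.

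Two stronger readings are not supported. One is that the rule favours the drug: that would need failures that differ by arm, and in a double-blind trial the documents give no reason to expect this. The other is that suppression of bleeding is affected to the same degree. Suppression requires no day above 2 mL (SAP 7.6.2 and 11.3.2.2), so its status changes only if every such day is lost.

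**What to change.** In SAP 7.6.1.1, before unblinding:

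1. Define NULL, IN ERROR, NO DATA and the other character codes, and say whether each applies to a day or to a collection.
2. State that a returned but unevaluable AH record is not counted as 0, and that the volume of every window containing one is missing. This must include the monthly windows that feed 11.2.2.1; otherwise the imputation could hand back the same understated Month 6 sum.
3. If the evaluable total is already at least 80 mL or more than 50% of Baseline, classify the subject as a non-responder.
4. For the Final Month, impute by 11.2.2.1 and take the larger of the imputed value and the evaluable total. Use that volume for responder status and for the ranked change to the Final Month. In the worked case, the floor would be 77 mL.
5. For the monthly MMRM endpoints, leave that month missing.
6. Report the number of partly unevaluable windows by arm, and add a sensitivity analysis that counts such Final Months as non-response.

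The cost is SAP wording, a flag built from codes already reported, slightly more imputed windows and one step after imputation. Taking the larger value afterwards avoids building subject-specific bounds into the imputation model.

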7.6.2 Bleeding Days

A bleeding/spotting day is defined as a day having daily MBL volume of > 0 mL.

A spotting day is defined as a day having daily MBL volume of $> 0 - 2$ mL.

A bleeding day is defined as a day having daily MBL volume of > 2 mL.

Bleeding intensity categories are

- Daily MBL volume of $> 2 - 10$ mL.
- Daily MBL volume of $> 10 - 40$ mL.
- Daily MBL volume of $> 40 - 80$ mL.
- Daily MBL volume of > 80 mL.

Please note that only observed AH data will be used for daily MBL volume categories above.

8.0 Demographics, Baseline Characteristics, Medical History, and Prior/Concomitant Medications

8.1 Demographic and Baseline Characteristics

Demographics and Baseline characteristics will be summarized for all randomized subjects who received at least one dose of study drug by treatment group.

8.1.1 Demographics

Continuous variables such as age, height, weight, and BMI will be summarized with the mean, standard deviation (SD), median, minimum, and maximum by treatment group and overall and also be compared among treatment groups using one-way analysis of variance (ANOVA). Number and percentage will be computed by treatment group and overall for

the following demographic parameters: age group (18 – < 20 years old, 20 – < 25 years old, 25 – < 30 years old, 30 – < 35 years old, 35 – < 40 years old, 40 – < 45 years old, 45 – < 50 years old, ≥ 50 years old), BMI (≤ 18.5 kg/m², > 18.5 kg/m² – < 25 kg/m², 25 kg/m² – < 30 kg/m², 30 kg/m² – < 35 kg/m², 35 kg/m² – < 40 kg/m², ≥ 40 kg/m²), sex, race, ethnicity, tobacco use (current, former, never, and unknown), and alcohol use (current, former, never, and unknown). Categorical variables will be compared among treatment groups using a Fisher's exact test.

The number and percentage of subjects with Baseline presence of adenomyosis (as defined in Section 11.3.5.3) will be summarized by treatment group and overall. No statistical tests will be performed.

Physician Surgery Questionnaire (PSQ)

For each of the PSQ questions ([Appendix G](#)), the number and percentage of subjects in each response category will be summarized at Baseline by treatment group and overall. No statistical tests will be performed.

Reason for Study Participation Questionnaire

Descriptive statistics will be presented for reasons for study participation for each treatment group. No statistical tests will be performed.

8.1.2 Baseline Characteristics

Menstrual Blood Loss (MBL)

Baseline MBL measured by AH method as defined in Section 7.1 will be summarized for each treatment group and overall with mean, SD, median, minimum, and maximum values. The baseline MBL values will be compared among treatment groups using one-way ANOVA.

Bleeding Days

Baseline for bleeding days will be based on the observed daily AH data in Screening as defined in Section 7.1 and Section 7.6.

The numbers of bleeding days by intensity categories at Baseline will be summarized with mean, SD, median, minimum, and maximum for each treatment group and overall.

Hemoglobin Concentration

Baseline hemoglobin concentration will be summarized for each treatment group and overall with mean, SD, median, minimum, and maximum values. The number and percentage of subjects with Baseline hemoglobin concentration in the following categories will be summarized for each treatment group and overall: ≤ 10.5 g/dL, $> 10.5 - \leq 12$ g/dL, and > 12 g/dL.

Fibroid and Uterine Volume

Baseline uterine volume, Baseline volume of the largest fibroid, and Baseline total fibroid volume (3 largest fibroids) will be summarized for each treatment group and overall with mean, SD, median, minimum, and maximum values and will be compared between each elagolix dose group and placebo using one-way ANOVA.

8.2 Medical History

Medical/surgical, gynecological, menstrual and obstetrical history will be summarized and presented using system organ classes (SOCs) and preferred terms (PTs) from the Medical Dictionary for Regulatory Activities (MedDRA) Version 19.0 or higher. Subjects reporting more than one medical history within a SOC will be counted only once for that SOC. Subjects reporting more than one medical history for a PT will be counted only once for that PT. No statistical tests will be performed on medical history.

8.3 Prior, Concomitant, and Post-Treatment Medications

Medications with a start date prior to the first study drug dose date will be counted as prior medication.

Concomitant medications are those medications, other than study drugs, taken during the treatment period with an end date after the first dose of study drug or ongoing at the end of study, and a start date prior to the last dose of study drug. A medication will be considered a concomitant medication where one of the following three cases occur (1) the start date is missing and the end date is either after or on the first study drug dose date; (2) the start date is not missing and the end date is missing; (3) both the start date and the end date are missing.

No statistical tests will be performed on prior medications and concomitant medications.

For prior medications administered to treat uterine fibroid symptoms, the following data are collected: dates of administration (including start and stop dates), dose, route, and reason for discontinuation. Prior medications will be summarized for all randomized subjects who received at least one dose of study drug with number and percentage for each treatment group and overall using ATC Classification and preferred terms from the World Health Organization (WHO) Drug Dictionary.

Concomitant medications for all randomized subjects who received at least one dose of study drug will be summarized using ATC Classification and preferred terms from the World Health Organization (WHO) Drug Dictionary with number and percentage for each treatment group and overall.

Other medications taken during the Post-Treatment Follow-up Period, which includes all medications with an end date after the last dose of study drug or ongoing at the end of study for subjects who did not enroll in the extension study, will be summarized by ATC Classification and WHO preferred term with number and percentage for each treatment group and overall.

A subject who reports two or more uses of the same medication will be counted only once within each WHO preferred term. A subject with medications with more than one generic name will be counted only once in the overall total. Prior medications, concomitant medications, and other medications during the Post-Treatment Follow-up Period will be summarized separately.

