For subjects entering the 12-month Post-Treatment Follow-Up Period, visits will be conducted either by phone or on-site from Month 1 through Month 12. (Subjects who prematurely discontinue from the Treatment Period prior to the Month 3 Study visit, are not required to have the pelvic ultrasound, MRI [if applicable] or DXA [unless the reason for discontinuation was due to BMD decrease or occurrence of fracture] performed in the Post-Treatment Follow-up Period and will complete the study at the Post-Treatment Follow-up Month 6 visit.) Post-Treatment Follow-up Months 1, 3, 6, 9 and 12 are on-site visits while Post-Treatment Follow-up Months 2, 4, 5, 7, 8, 10 and 11 are Phone Visits.

During the phone visits, site personnel will discuss adverse events, concomitant medications, if applicable, obtain the results of the subject's self-administered urine pregnancy test and will remind subjects of the importance of consistent use of appropriate and effective dual non-hormonal contraception through the Post-Treatment Follow-Up Period. Subjects may begin taking hormonal contraception or Tranexamic Acid (Lysteda, Cyklokapron, Cyclo-f) after completing the Post-Treatment Follow-Up Month 2 Visit and having returned to first full menses in the Post-Treatment Follow-up Period.

Subjects will be required to collect sanitary products for the first full menses in the Post-Treatment Follow-up Period. Subjects will return the sanitary products at a Product Collection Visit within approximately 5 days after cessation of bleeding or spotting.

During the Post-Treatment Month 3 and Post-Treatment Month 6 on-site visits, procedures such as TAU, TVU, MRI (if applicable), DXA, clinical safety labs and pregnancy testing will be performed. At the Post-Treatment Period Month 12 visit, procedures including vital signs, lipid panel, Apolipoprotein A and B and DXA will be performed.

Adverse event and concomitant medication review will be conducted at all visits during the Post-Treatment Follow-Up Period, including the phone visits.

Central Laboratory and Central Imaging Vendors:

DXA, Ultrasound, SIS, MRI (if applicable), safety clinical lab samples including Apo A, and Apo B, endocrine panels, and alkaline hematin will be analyzed/evaluated using central laboratories or vendors. Assays for PK, PD and PG will be analyzed at AbbVie.

Analysis of Menstrual Blood Loss:

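### SAP 8.3 contradicts itself: case (2) of the missing-date rule sets no limit on the start date, so a drug first started in follow-up could be counted as concomitant

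*SAP*

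**What the plan says.** SAP 8.3 gives the definition first: "Concomitant medications are those medications, other than study drugs, taken during the treatment period". It goes on to require an end date after the first dose or an ongoing record, "and a start date prior to the last dose of study drug".

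The next sentence adds a rule for incomplete dates: "A medication will be considered a concomitant medication where one of the following three cases occur". The first case is "1) the start date is missing and the end date is either after or on the first study drug dose date". The second is "2) the start date is not missing and the end date is missing". In the third, both dates are missing.

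The same section plans a separate table for drugs used in the Post-Treatment Follow-up Period. It takes in drugs that end after the last dose or are "ongoing at the end of study for subjects who did not enroll in the extension study". Prior, concomitant and post-treatment medications are to be summarised separately, and no statistical tests are planned on prior or concomitant medications.

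The protocol makes such records possible. Its synopsis states: "Subjects may begin taking hormonal contraception or Tranexamic Acid (Lysteda, Cyklokapron, Cyclo-f) after completing the Post-Treatment Follow-Up Month 2 Visit", provided the first full menses has returned. Protocol 5.2.3.2 has medications from all periods, follow-up included, entered on the Concomitant Medication eCRF.

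**The concern.** The definition bounds the start date from above. Case (2) does not, although its start date is known and could be tested. For a drug with a known start after the last dose and no end date, one sentence excludes it and the next includes it. The content of the table then depends on which sentence the programmer codes.

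What is at stake is the accuracy of the concomitant-medication table. A reader would look there for on-treatment use of drugs that change bleeding, which Protocol 5.2.3.5 prohibits on treatment and allows later. The same drug would also appear in the post-treatment table, although the two are meant to separate treatment from follow-up. The problem is not limited to hormonal drugs: any drug first started in follow-up and left without an end date meets case (2).

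**Working it through.** The SAP gives no figure to reproduce. The check applies each sentence to test records. First dose is Day 1 and last dose Day 168 (six 28-day months); the drug dates are illustrative.

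**Is a Day 240 start allowed?** The nominal Post-Treatment Month 2 visit is Study End Day 56 (SAP Table 1), with a window of ±7 days (Protocol Table 1). The latest in-window visit is therefore on Day 168 + 56 + 7 = 231. A start on Day 240 falls after it, so it is permitted once menses has returned.

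**Rules applied**
- Definition: start before Day 168, and either end after Day 1 or ongoing.
- Cases: (1) start missing and end on or after Day 1; or (2) start known and end missing; or (3) both missing.
- Amended: meets the definition, or meets one of the cases with case (2) also requiring a start before Day 168.

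| Record | Definition | Three cases | Amended |
|---|---|---|---|
| Start Day −100, ongoing, no end date | yes | yes (2) | yes |
| Start Day 50, ongoing, no end date | yes | yes (2) | yes |
| Contraceptive, start Day 240, ongoing, no end date | **no** | **yes (2)** | no |
| Start Day 240, end missing, not marked ongoing | **no** | **yes (2)** | no |
| Tranexamic acid, Day 240 to Day 250 | no | no | no |
| Start Day −100, end missing, not marked ongoing | not shown | yes (2) | yes |
| Start missing, end Day 250 | not shown | yes (1) | yes |

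The conflict is confined to the third and fourth rows: a known start after the last dose with no end date. In the last two rows the definition cannot be evaluated, and the cases do their proper job of classing an uncertain record as concomitant. The amendment changes only the two conflicting rows.

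**Can the definition be read as limiting the cases?** If the cases applied only to records that already meet the definition, cases (1) and (3) could never be met, because a missing start cannot be shown to precede the last dose. The cases therefore read as stand-alone sufficient conditions. Case (1) has its own date bound; case (2) has none.

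**The case against.** The strongest reply is that the definition comes first and excludes the Day 240 drug outright. All three cases concern missing dates, so they can be read as conventions for records on which the definition cannot be evaluated. On that reading a known post-treatment start is never concomitant. This stands in part. A reader might infer that every open-ended drug started in follow-up will be tabulated as used on treatment, but the documents do not settle that: the SAP contains both the exclusion and the inclusion. It does not remove the defect, because the wording makes any one case sufficient.

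Second, SAP 8.3 speaks of drugs that are ongoing and of end dates that are missing without saying that the first is stored as the second, and Protocol 5.2.3.2 requires end dates to be recorded. This stands: for ongoing drugs the problem depends on an unstated coding convention. Tranexamic acid is a weaker example than a contraceptive. Protocol 3.1 describes its use as short-term, and a completed course has an end date.

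Third, a reader might infer that the bleeding results are put in doubt. They are not. SAP 4.4 makes the end-of-treatment analysis the only analysis of the primary and ranked secondary endpoints and excludes follow-up data from it. Responder status (SAP 11.2.1), the imputation model (11.2.2.1) and the analysis sets (5.1) do not use concomitant-medication status.

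Fourth, a reader might infer a size or a difference between arms. Guessing that 40–50% of an arm enters follow-up and that 10–30% of these start an open-ended drug gives 0.40 × 0.10 = 4% to 0.50 × 0.30 = 15%. Neither factor is in the documents, and the product also presumes literal programming and blank end dates. Women with a BMD decrease of 8% or more cannot enter the extension. In Phase 2b, at the lumbar spine, that was 8% on elagolix alone and none with standard-dose E2/NETA (Protocol 3.2.2). This is only one route into follow-up, and it says nothing about which drugs are started there, so it does not show that any arm would look worse.

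**Conclusion.** The contradiction is real and the rule is wrong as written. Case (2), applied literally, classes a drug with a known start after the last dose and no end date as concomitant, against the definition in the preceding sentence. Wrong counts would reach a reported table if two conditions hold: the cases are coded as sufficient on their own, and the record has no end date (for an ongoing drug, because ongoing is stored that way).

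The effect is limited to descriptive medication tables that include follow-up data, for women who did not enter the extension. No hypothesis test, error rate, primary result or ranked secondary result is touched. How many women would be miscounted cannot be derived from the documents. The correction is worth making because it is exact and nearly free, not because the consequence is large.

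**What to change.** In SAP 8.3, reword case (2) so that it requires a known start date that precedes the last dose of study drug, together with a missing end date. Add one sentence stating that a medication with a known start after the last dose is post-treatment only.

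Keep the definition's strict boundary in case (2), so that no new mismatch arises for a drug started on the last-dose date itself. If the team wants that day counted as concomitant, both sentences should change together. It would also help to say whether an ongoing record is treated as having a missing end date.

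The cost is one clause and one or two sentences in SAP 8.3, plus a check that the table program follows them. No data collection or efficacy analysis changes, and drugs started before the last dose keep their present classification.
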